5.3 Randomisation and Blinding

Biases and blinding

- Randomisation controls for performance and incorporation biases with respect to the clinical utility of bpMRI in comparison to mpMRI.
- Pathologists will be blinded to MRI type by ensuring the pathology request forms do not provide this information.

Imaging scan data

IP7-PACIFIC	Protocol No: 22CX7488	Imperial College London	V3.0 18 th December 2023

Imaging scans are performed as part of this study. We will also ask for consent from patients to store and use their scan data in future research (academic or commercial) to see if new ways of looking at these scans can detect cancer better in the future. All scans need to be electronically transferred for collation at Imperial in order to facilitate double reporting and therefore will be available for data banking within the Research Data Store (https://www.imperial.ac.uk/admin-services/ict/self-service/research-support/rcs/rds/).

Randomisation process

In randomisation-1, patients with suspected prostate cancer will be allocated in a 1:1 ratio to bpMRI or mpMRI, and those with a suspicious MRI (either bpMRI or mpMRI) who are recommended to undergo targeted biopsy will be allocated 1:1 to image-fusion or visual-registration biopsy (along with non-targeted systematic biopsy as per guidance). Randomisation-2 will be stratified for type of MRI to which participants in the first randomisation are allocated.

	Screening			
Visit	1	2	3	4
Week	0	1-8	1-8	2-12
Informed consent	Х			
Inclusion & exclusion criteria	Х			
Demographics	Х			
Targeted medical history	X ¹			
MRI		Х		
Biopsy (in some patients)			X ²	
Patient questionnaires	X ³	X ³		X ³
Biopsy results				X4
Adverse events			X ⁵	X ⁵

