2.3 Primary Endpoint

Randomisation-1: bpMRI versus mpMRI

Proportion of clinically significant cancers, defined as any amount of Gleason >/=3+4 (ISUP Grade Group >/=2) on biopsy, detected in the randomised population of patients at risk.

Randomisation-2: Visual-registration targeting versus image-fusion targeting

Proportion of clinically significant cancers, defined as any amount of Gleason >/=3+4 (ISUP Grade Group >/=2) on biopsy, detected in the randomised population of patients biopsied for a suspicious MRI.

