Expertise: There are no guidelines on what level of biopsy experience is required by clinicians in the NHS nor whether there should be minimum annual numbers for being designated as competent in targeted biopsy. Therefore, a robust study-specific standardisation programme will be used for all clinicians carrying out biopsy. For those centres using certain biopsy image-fusion devices, company-specific training modules and competency sign-off will need to occur. Whilst a minimum number of targeted biopsies has not been recommended in any guideline, our clinical opinion from experienced biopsy operators is that a minimum of 100 cases should have been carried out using the technique being proposed. We will also record the experience of each biopsy operator in terms of number of biopsies (to the nearest 50), years of experience and the specialty of operator (radiology, urology, nursing).

IP7-PACIFIC Protocol No: 22CX7488	Imperial College London	V3.0 18 th December 2023
-----------------------------------	-------------------------	-------------------------------------

Targeting and systematic biopsy protocol: We will follow standard care for centres in terms of type of analgesia/anaesthesia. Our clinician survey shows centres are using local anaesthetic, sedation or general anaesthetic; transperineal or transrectal route and visual-registration or image-fusion targeting. The exact anaesthesia type (local only, sedation, general anaesthetic) will be recorded. Number of systematic cores will be as described above with 6 cores per target (divided into 4+2 for the first lesion only) and unlimited targets in total per patient [Hansen et al, 2020; Leyh-Bannurah et al, 2020; Kenigsberg et al, 2018]. Targeted biopsies will be carried out first, in order to minimise the impact of swelling on obtaining accurate sampling of targets.

Histology

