The histological report will evaluate the following aspects for each target and each location of systematic biopsies carried out according to Royal College of Pathology (UK) guidance [Royal College of Pathology Guidelines, 2016]: number of biopsies, number positive for cancer, core length in mm, cancer presence, maximum cancer core length in mm (where continuous and discontinuous numbers are given, for the purpose of analysis, the continuous number will be used), primary, secondary and highest Gleason grade, percent pattern 4 and presence of cribriform pattern when Gleason 3+4, perineural invasion/lymphovascular invasion/intraductal components/neuroendocrine differentiation; and vii) other features (high grade prostatic intraepithelial neoplasia/atypical acini/inflammation/atrophy). See Biopsy Reporting SOP.

Definition of clinically significant prostate cancer on histology

We know that some prostate cancers are clinically significant, and that other prostate cancers are clinically insignificant. Whilst there is still some uncertainty about exactly what entails clinical significance, particularly with respect to whether patients diagnosed with low volume Gleason 3+3 or Gleason 3+4 cancer should be on active surveillance, most physicians, researchers and guideline panels agree detection of Gleason >/=3+4 (ISUP grade Group >/=2) is the key target condition for any screening or diagnostic pathway. As a result, this is the primary histological threshold we will measure.

There is also acknowledgement that a low amount of cancer or low percent pattern 4 is perhaps not as aggressive. So, whilst the primary outcome measure will be the detection of any Gleason >/=3+4, there are important secondary definitions of clinical significance that we will measure as well. These definitions will incorporate the wide and divergent views on clinical significance but incorporate evidence on the amount of pattern 4 and maximum cancer core length as being significant elements [26-30]. These definitions will be:

- any amount of Gleason 4+3=7 or more
- any amount of Gleason >/=4+3 OR Gleason 3+3=6 of >/=6mm (PROMIS definition 1)
- any amount of Gleason >/=3+4 OR Gleason 3+3=6 of >/=4mm (PROMIS definition 2)
- any amount of Gleason >/=3+4 OR Gleason 3+3=6 of >/=6mm (PROMIS definition 3)

- any amount of Gleason 3+4=7 with cribriform pattern or a ductal component or >/=10% pattern 4 or any Gleason >/=4+3 [van Leenders et al, 2020].

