5.4 Visit Schedule

¹ Prostate MRI or prostate biopsy in the past and outcome (occurring more than 2 years prior to screening visit), current use of 5-alpha reductase inhibitors (e.g., finasteride or dutasteride), use of testosterone supplementation or androgen suppression medication, family history of prostate cancer (defined as any immediate family relative diagnosed with prostate cancer at any time), ethnicity (using the UK Office for National Statistics groupings). ² Biopsy may occur on same day as MRI in some centres

3 Questionnaires which require baseline data will be given for completion before the MRI or biopsy. The schedule of questionnaires is referenced in section 5 Validated patient reported outcome measures and also within the Patient Reported Outcomes and Experience Questionnaire.

4 Adverse events will be assessed up to Visit 4 after first randomisation by electronic questionnaire sent by the central trial team directly to the patient via the RedCap system or given to the patient by local site on printed paper. Additionally, any adverse events noted by the local clinical team on patient records will be recorded in the eCRF where applicable. 5 Biopsy outcomes will be assessed from clinical report directly from medical records

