8. STATISTICAL ANALYSES

8.1 Sample Size and power considerations

Randomisation 1: bpMRI vs mpMRI

Consistent with NIHR-HTA PROMIS [[name] et al, 2017], NIHR PRECISION observed a 38% detection of clinically significant prostate cancer (defined as any Gleason >/=3+4 [ISUP Grade Group >/=2]) in patients with suspected prostate cancer having pre-biopsy mpMRI compared to 26% having a traditional biopsy alone without pre-biopsy MRI [Kasivisvanathan et al, 2018]. To preserve at least 50% of the improvement in detection rates implies exclusion of a 6% absolute reduction from a 38% detection rate in order to recommend a switch from mpMRI to bpMRI. We have chosen a non-inferiority margin of 5% which strikes a balance between our clinician survey, the patient perspective, ensuring improvement on the previous standard of care and an achievable sample size. To provide 90% power to confirm non-inferiority and exclude an absolute 5% reduction in detection rate of clinically significant prostate cancer from an estimated 38% in both arms, using an overall 0.05 significance level for a one-sided test, requires 3230 men (1615/arm). A target sample size of 3600, would therefore account for an assumed attrition rate of about 10%.

IP7-PACIFIC Protocol No: 22CX7488	Imperial College London	V3.0 18 th December 2023
-----------------------------------	-------------------------	-------------------------------------

The expected detection rates of clinically significant prostate cancer (defined as any Gleason >/=3+4 [ISUP Grade Group >/=2])are 55% (visual-registration) and 65% (image-fusion). Our clinician and patient groups indicated that >/=10% improved detection rate using image-fusion is acceptable for adoption. In PRECISION and PROMIS, approximately 70-75% were recommended for biopsy following mpMRI. Assuming 70% will be recommended for biopsy and conservatively assuming a further 10% attrition, we anticipate at least 2000 patients from randomisation-1 would be eligible for randomisation-2. This provides ample power (>95%) to detect the absolute 10% difference described above using a two-sided test at the 5% significance level. Include the number of subjects to be enrolled, reason for choice of the sample size, including details of the sample size estimation and the power of the study and clinical justification.

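### Pathologists are masked to MRI type, but the protocol provides no masking to targeting method, the contrast that randomisation 2 tests

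*Protocol*

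**What the plan says.** Protocol section 5.3 (Randomisation and Blinding) lists two safeguards under biases and blinding. The first says that randomisation protects the comparison of bpMRI with mpMRI. The second is "Pathologists will be blinded to MRI type by ensuring the pathology request forms do not provide this information". Both concern randomisation 1.

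The same section then describes randomisation 2, in which patients with a suspicious MRI who are recommended for targeted biopsy "will be allocated 1:1 to image-fusion or visual-registration biopsy". No masking to that allocation is described there or elsewhere in the Protocol.

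Section 2.3 gives both randomisations the same endpoint definition, any Gleason >=3+4 on biopsy. For randomisation 2 it is counted as "detected in the randomised population of patients biopsied for a suspicious MRI".

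On how the reading is obtained:
- A footnote to the visit schedule (section 5.4) says "Biopsy outcomes will be assessed from clinical report directly from medical records".
- Section 5 (Histology) says "The histological report will evaluate the following aspects for each target and each location of systematic biopsies carried out" and refers further detail to a Biopsy Reporting SOP.
- Sections 5 and 5.3 plan double reporting for MRI scans. No second or central read is described for histology.

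Section 5 sets the targeted sampling "with 6 cores per target (divided into 4+2 for the first lesion only) and unlimited targets in total per patient", with no distinction between arms. All patients in randomisation 2 also have systematic cores.

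**The concern.** The operator necessarily knows which targeting technique was used. The pathologist does not need to, and the pathologist's grade decides the primary outcome. By taking MRI type off the request form, the sponsor has already judged that knowledge of allocation could colour that grade. The same reasoning applies to randomisation 2, which has the same endpoint and is a superiority comparison, yet the rule stops at MRI type.

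What matters is grading that differs by arm, mainly at the boundary between 3+3 and 3+4. Grading error unrelated to arm would not favour either method. A difference linked to arm would add directly to the estimated risk difference, and a larger sample would not dilute it. It would also carry into the secondary histological thresholds and the cost per clinically significant cancer detected.

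**Working it through.** **Inputs from Protocol section 8.1:** expected detection of 55% (visual-registration) and 65% (image-fusion); at least 2000 patients for randomisation 2; two-sided 5% test; power above 95%. Allocation is 1:1 (section 5.3), so 1000 per arm.

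**Input not in the Protocol:** the size and direction of any grading shift by arm. This is assumed, and the range starts at zero.

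**Step 1, the plan's own figures.**
- Patients available: 3600 × 0.9 × 0.7 × 0.9 = 2041, consistent with at least 2000.
- Power: the pooled standard error at 60% is sqrt(2 × 0.60 × 0.40 / 1000) = 0.02191. The unpooled standard error is sqrt((0.55 × 0.45 + 0.65 × 0.35) / 1000) = 0.02179. Power = Φ((0.10 − 1.96 × 0.02191) / 0.02179) = Φ(2.62) = 99.6%, which agrees with the stated figure. The sample size is not in question.

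**Step 2, precision under no true difference.** At 55% in both arms, SE = sqrt(2 × 0.55 × 0.45 / 1000) = 0.02225, or 2.2 points. Significance needs an observed difference of about 1.96 × 2.225 = 4.4 points.

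**Step 3, effect of an assumed shift b.** The chance of a significant result is P(Z > 1.96 − b/SE) + P(Z < −1.96 − b/SE).

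| b (points) | b/SE | upper tail | lower tail | two-sided type I error | b as share of the 45% without significant cancer |
|---|---|---|---|---|---|
| 0 | 0 | 2.5% | 2.5% | 5% | 0% |
| 1 | 0.449 | 6.5% | 0.8% | 7.3% | 2.2% |
| 2 | 0.899 | 14.4% | 0.2% | 14.6% | 4.4% |
| 3 | 1.348 | 27.0% | <0.1% | 27% | 6.7% |

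The last column is b/0.45. It is the share of patients otherwise below the threshold who would have to be graded at or above it in one arm only. Because the endpoint counts any core, these must be patients in whom no other core, targeted or systematic, already reaches 3+4.

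**Step 4, can the masking be extended?** The listed report content in section 5 needs the site and the lesion, and nothing in it calls for the targeting method. The number of cores per target is stated without distinction by arm, so the sampling as described need not reveal the method.

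**The case against.** The strongest reply is that silence is not disclosure. A reader might infer that pathologists will know the targeting method. The Protocol does not say so, and the Biopsy Reporting SOP, which is not available here, may already withhold it. That stands, and it limits the point to this: no masking to targeting method is provided for in the Protocol.

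Other tempting readings also go beyond the document:
- That the readers are local pathologists. This is only inferred from the use of clinical reports.
- That specimen labels are identical in both arms. Labelling is not described, and because the number of targets is unlimited, total cores vary between patients.
- That a change to the form removes the bias. It closes one route. The method could still be learned from the biopsy record or in multidisciplinary discussion.
- That a small shift is enough to reach significance. About 4.4 points must be observed. With a 3-point shift and no true effect, about 73% of trials would still be non-significant.

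Two further arguments carry some weight. Reporting follows Royal College of Pathology guidance, and radiologist certification asks about compliance with WHO/ISUP pathology standards. Both constrain grading, though neither is masking. Also, section 8.1 describes a gain of at least 10 points as what clinicians and patients would accept for adoption. Under a 3-point shift with no true effect, a difference that large would be observed about 0.1% of the time (z = 7/2.225 = 3.15). The 10 points are not a test threshold, however, and the planned analysis reports a p-value and a confidence interval, both of which a shift would affect.

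**Conclusion.** The point holds as a gap in masking, not as evidence of bias. The Protocol addresses masking of the outcome assessor explicitly, but for only one of its two primary comparisons, although both rest on the same graded reading and no second histology read is described. This belongs in the Protocol and is not a detail normally left to the SAP.

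The possible consequence runs from nothing (5% type I error if there is no shift by arm) to 7.3%, 14.6% or 27% for assumed shifts of 1, 2 or 3 points. These figures rest on 1000 patients per arm, 55% detection, no true difference and a shift in one consistent direction across centres. The document supports neither a size nor a direction, so they show the sensitivity of the design and are not a forecast. The stated power and sample size are unaffected.

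**What to change.** Extend the sentence in section 5.3 so that pathology request forms and specimen labels carry neither the MRI type nor the targeting method, and identify each specimen only as target or systematic, with site and lesion number. Put the same line in the Biopsy Reporting SOP. If the SOP already contains it, section 5.3 need only say so.

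The cost is wording in a form and an SOP. No extra reader is needed, and the sample size does not change. The downside is that the targeting method must be recorded in the operative record and the eCRF instead of on the request. Some risk of unmasking remains through the biopsy record and multidisciplinary discussion.

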5.4 Visit Schedule

¹ Prostate MRI or prostate biopsy in the past and outcome (occurring more than 2 years prior to screening visit), current use of 5-alpha reductase inhibitors (e.g., finasteride or dutasteride), use of testosterone supplementation or androgen suppression medication, family history of prostate cancer (defined as any immediate family relative diagnosed with prostate cancer at any time), ethnicity (using the UK Office for National Statistics groupings). ² Biopsy may occur on same day as MRI in some centres

3 Questionnaires which require baseline data will be given for completion before the MRI or biopsy. The schedule of questionnaires is referenced in section 5 Validated patient reported outcome measures and also within the Patient Reported Outcomes and Experience Questionnaire.

4 Adverse events will be assessed up to Visit 4 after first randomisation by electronic questionnaire sent by the central trial team directly to the patient via the RedCap system or given to the patient by local site on printed paper. Additionally, any adverse events noted by the local clinical team on patient records will be recorded in the eCRF where applicable. 5 Biopsy outcomes will be assessed from clinical report directly from medical records

5.5 Follow-up

Any incidental findings should be identified at the study visits and reviewed by the site teams and if necessary will be reported to the clinical care team and subjects GP.

These reflect standard care and there will be no additional follow-up visits required for the study.

6. INTERVENTION

6.1 Permanent Discontinuation of Study Intervention and Withdrawal from Study

(i) Permanent discontinuation of study intervention

Subjects may discontinue study intervention for the following reasons:

- At the request of the subject.
- Adverse event/ Serious Adverse Event
- If the investigator considers that a subject's health will be compromised due to adverse events or concomitant illness that develop after entering the study.

(ii) Withdrawal from Study

Withdrawal from the study refers to discontinuation of study intervention and study procedures and can occur for the following reasons:

- Subject decision
- Loss to follow-up

(iii) Procedures for Withdrawal from Study

Patients may decide to opt out of IP7-PACIFIC at any time. This is entirely within their right to do so. Such cases will be reported to the Research Team Office so that no further data are entered onto the database, as specified in the patient information leaflet and appropriate Standard Operating procedure. Data captured before consent was withdrawn will be used in the study, but no further data, beyond this date will be collected or used in any analysis. Reason for withdrawal should be recorded in the eCRF and medical records, if given by the patient. Our sample size calculation assumes a 10% withdrawal rate but if this exceeds that number, we will continue to recruit patients until the target number for each randomisation is met.

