For each randomisation, the number and proportion of clinically significant cancers detected in the randomised population will be reported by trial arm. Group differences will be quantified by the risk difference with two-sided confidence intervals at a level appropriate to the significance level pre-specified in the sample size. Detection rates will be compared by trial arm using mixed models with adjustment for trial arm allocation of co-enrolled trial and random effect by centre. The treatment effect coefficients will be presented with confidence intervals and associated p-value. The primary analysis will be conducted on an intention-totreat (ITT) basis, where patients with missing outcomes are assumed not to have clinically significant prostate cancer. A modified ITT analysis will be performed excluding patients who did not complete the diagnostic tests, and for the non-inferiority comparison a per protocol analysis including only those undergoing randomly assigned interventions. A pre-specified statistical analysis plan will be drafted detailing intended analyses for primary and secondary outcomes. It will be approved by the IDMC and agreed prior to analysis.

Cost-effectiveness analysis

A within trial cost-effectiveness analyses will estimate the incremental cost per true positive detected and incremental cost per correct diagnosis. Estimates of diagnostic performance will be based on the trial analysis and costs will be estimated from the NHS and PSS perspective using a micro-costing approach for tests. Deterministic (to explore plausible alternatives e.g., quantity of resources used or unit costs) will be combined with stochastic

IP7-PACIFIC Protocol No: 22CX7488	Imperial College London	V3.0 18 th December 2023
-----------------------------------	-------------------------	-------------------------------------

sensitivity analysis (used to explore statistical imprecision in estimates of costs, effects and cost-effectiveness).

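### Opting out stops all data collection, with no stated option to keep record review, so primary outcomes obtainable from routine records can be lost and scored as no significant cancer

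*Protocol*

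**What the plan says.** Protocol section 6.1 has three parts.

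- **Part (i)** covers permanent discontinuation of the study intervention, including at the man's own request. It attaches no data stop, and it does not say that record review continues.
- **Part (ii)** covers withdrawal from the study: "Withdrawal from the study refers to discontinuation of study intervention and study procedures". It lists two reasons, the subject's decision and "Loss to follow-up".
- **Part (iii)** is the only withdrawal procedure. It is worded for men who opt out. Nothing more is entered on the database. Data captured before consent was withdrawn are kept, but "no further data, beyond this date will be collected or used in any analysis".

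Two other places determine what follows. A footnote to the visit schedule in section 5.4 says "Biopsy outcomes will be assessed from clinical report directly from medical records". Section 8.3 says that in the primary ITT analysis "patients with missing outcomes are assumed not to have clinically significant prostate cancer". Section 8.3 also plans a modified ITT analysis that leaves out men who did not complete the diagnostic tests and, for the non-inferiority comparison, a per-protocol analysis.

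**The concern.** The primary outcome needs nothing more from the man once he has been biopsied, because the result is in the hospital pathology report. A man may be tired of the questionnaires or of study procedures in general, yet have no objection to that report being read. Section 6.1(iii) gives him no stated way to say so. If he opts out before his histology is captured and is then biopsied in normal care, a Gleason 3+4 or higher result sits in his record, may not be collected, and is scored in the primary analysis as not detected.

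The rule decides which data exist, so no later analysis plan can restore what it forbids collecting. The provision in section 6.1 to continue recruiting if withdrawal exceeds 10% adds men but does not remove the imputed negatives.

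The randomisation 1 comparison is a non-inferiority test. Scoring missing outcomes as negative in both arms pulls the two detection rates together, which makes non-inferiority easier to claim. If men leave one arm more than the other, the comparison shifts directly. Section 5.3 describes blinding of pathologists only, so leaving could depend on arm. The protocol gives no reason to expect a particular direction.

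**Working it through.** **Inputs, all from the protocol.** Section 8.1: 90% power; margin 5 points absolute; detection "from an estimated 38% in both arms"; one-sided 0.05; 1615 per arm (3230 in all); target 3600 for about 10% attrition. Section 6.1: 10% withdrawal assumed. Section 8.3: missing counts as no clinically significant cancer. Section 5.3: allocation 1:1, hence 1800 per arm.

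**1. Reproduce the stated size.** n per arm = (1.645 + 1.282)² × 2 × 0.38 × 0.62 / 0.05² = 1614.1, rounded up to 1615, or 3230 in total. Inflation for attrition: 3230 / 0.90 = 3589, against a target of 3600. The design reproduces.

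**2. Ceiling on the number affected.** 3600 × 0.10 = 360 men. At 38% detection, 360 × 0.38 ≈ 137 significant cancers. This assumes that every man in the 10% leaves before his result is captured, and that all are worked up in routine care with the usual detection rate.

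**3. Effect of equal loss on the non-inferiority test.** Let a fraction d in each arm be missing and scored negative. Each arm's expected rate is then multiplied by (1 − d). Put the truth at the margin: 38% mpMRI, 33% bpMRI. With D the expected observed deficit,

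SE = √[p₁(1 − p₁)/1800 + p₂(1 − p₂)/1800]

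P(claim non-inferiority) = Φ[(0.05 − D)/SE − 1.645]

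| Missing, each arm | Expected rates | D (points) | False non-inferiority |
|---|---|---|---|
| 0% | 38.0% v 33.0% | 5.00 | 5.0% |
| 2% | 37.2% v 32.3% | 4.90 | 5.7% |
| 5% | 36.1% v 31.4% | 4.75 | 6.9% |
| 10% | 34.2% v 29.7% | 4.50 | 9.3% |
| 15% | 32.3% v 28.1% | 4.25 | 12.4% |

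For the 10% row: SE = 0.01552; (0.05 − 0.045)/0.01552 = 0.322; Φ(0.322 − 1.645) = 0.093.

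The same table shows what retrieval buys. Recovering half of a 10% loss is the 5% row (6.9%). Recovering 80% is the 2% row (5.7%).

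**4. Unequal loss, with assumed splits.**

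- *12% mpMRI, 8% bpMRI, true 5-point deficit.* Rates 0.38 × 0.88 = 0.334 and 0.33 × 0.92 = 0.304; D = 3.1 points; SE = 0.0155; Φ(1.236 − 1.645) = 0.34.
- *8% mpMRI, 12% bpMRI, true 5-point deficit.* Rates 0.350 and 0.290; D = 5.9 points; Φ(−0.593 − 1.645) = 0.013.
- *8% mpMRI, 12% bpMRI, arms truly equal at 38%.* Rates 0.350 and 0.334; D = 1.5 points; SE = 0.0158; power = Φ(2.201 − 1.645) = 0.71, against 93% with nothing missing at 1800 per arm.

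**The case against.** **A reader might infer that a man merely lost to follow-up also has his records closed.** The protocol does not say that. Part (ii) classes him as withdrawn, but the data stop in part (iii) is worded for men who opt out and dates from withdrawn consent, and he has done neither. What remains is an ambiguity: a site cannot tell from section 6.1 whether it may still retrieve his pathology report.

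**A reader might infer that a man who only refuses his allocated scan or targeting method is cut off.** That is also too strong. Part (i) covers stopping the intervention at the man's request, with no data stop. However, part (i) does not say that collection continues, and its wording overlaps with the subject's decision in part (ii). The missing piece is an explicit record-review option, above all for men who leave study procedures altogether.

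**A reader might infer that such men are analysed as cancer-free.** The assumption is no clinically significant cancer, and it applies in the primary ITT analysis only. Results captured before withdrawal are kept. The modified ITT analysis excludes men who did not complete the tests; if leaving is unrelated to outcome, excluding the missing men would hold the error at about 5%. It is a secondary analysis, though, and it does not recover any results.

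**Ending new collection when consent is withdrawn is a legitimate consent position.** This stands. The criticism is that one rule covers every way of opting out. Part (iii) also refers to the patient information leaflet and an operating procedure, neither of which is at hand. They may offer levels of withdrawal, but the protocol states none.

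**The figures lean on the missing-equals-negative rule and on a worst case.** Both are true. Section 5.4 allows biopsy on the day of the MRI, so some men would leave after their outcome is known, and some would never be biopsied. The 360 and 137 are upper limits. No passage supports either unequal split, and the two splits act in opposite directions.

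**Conclusion.** The point holds in a limited form. As written, section 6.1(iii) discards primary outcomes that could be read from routine records for men who opt out before histology is captured, and section 8.3 scores them as no clinically significant cancer in the primary analysis. For men lost to follow-up, the text is unclear; it does not impose a data stop on them.

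The size depends on how many outcomes are really lost, which the protocol does not give. With equal loss, false non-inferiority at the margin goes from 5.0% to 5.7%, 6.9% and 9.3% at 2%, 5% and 10% missing. With unequal loss it could reach about 34% (12% mpMRI, 8% bpMRI), or the reverse split could cut power to about 71% when the arms are equal. It cannot be said that the rule always favours bpMRI.

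These figures assume 1800 per arm, the same underlying detection rate in men with missing outcomes, a normal approximation, and no centre effect or covariate adjustment. They are worked for randomisation 1 only. The issue is worth correcting, because the lost data are obtainable and the correction is cheap.

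**What to change.** Amend section 6.1 to separate three situations:

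- **(a)** The man stops the allocated intervention, study procedures or questionnaires, but agrees that MRI, biopsy and histology results may be taken from routine records.
- **(b)** The man is lost to follow-up. State that this is not withdrawal of consent, take it out of the withdrawal reasons, and have sites retrieve the pathology report.
- **(c)** The man withdraws consent to any further data.

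Apply the data stop only to (c), and keep data captured before that date as now. Record the level on the eCRF, and use the same levels in the information sheet and the operating procedure to which section 6.1 refers.

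The cost is one ethics and information-sheet amendment, one eCRF field, and record checks of the kind sites already make for other participants. A man's right to stop all use of new data is unchanged.
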